Rapid population aging is increasing the number of older adults who suffer from motor-cognitive declines and associated increases in fall risk and fear of falling. Effectiveness of exercise, as an effective intervention to preserve cognitive function, has been well established and supported by recent studies including systematic reviews and our own prior work. But at the same time individuals with poor motor and cognitive performance generally cannot have regular visits to a rehabilitation center for face-to-face exercise, have highest drop out because of functional limitations, and have poorest adherence to unsupervised exercise programs. Therefore, designing a remote exercise intervention, tailor for those with cognitive impairment, is desperately needed and could make a significant impact in the field, including preserving cognitive function in people with MCI, promoting independent living, and reducing costs associated with consequence of cognitive-motor decline including falls and frailty. We propose to develop an in-home exercise system for adults with mild cognitive impairment or mild dementia that is specifically designed to improve balance and cognition during distractive conditioning while the exercise is remotely supervised by a telemedicine interface.

Section D: Purpose and Objectives

This research study aims to help design and validate a novel technology to remotely provide exercise intervention for people at risk or with some level of dementia. In addition, the platform enables remote assessment of cognitive-motor performance via wearable sensors through playing a simple interactive game named iTMT. A remote exercise intervention tailored to those with cognitive impairments could make significant impact in preserving cognitive function in people with MCI, promoting independent living, and reducing costs associated with consequence of cognitive-motor decline including falls and frailty. This application could in addition further the knowledge in use and development of remote technology to screen cognitive and motor performance and promote independent living in older adults in particular for those who are suffering from cognitive impairment and dementia. Given the large and growing number of older people at risk of developing cognitive impairment and dementia, this knowledge would be important to health providers, clinicians, older people, and their caregivers.

Section E: Protocol Risks/Subjects

E1. Risk Category

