Please indicate why you chose the sample size proposed:

For Phase I: Considering the timeline and budget limitation, the sample size is limited to 15 subjects. Size was estimated based on preliminary study, described in detail in the research strategy document, in which we have demonstrated that 4-weeks exergame program significantly reduce center of mass (COM) sway in aMCI patients with an effect size of 0.83 compared to baseline. Assuming a pairwise comparison using t-test, 80% power, alpha of 5%, 14 subjects should be sufficient to observed significant difference in balance compared to baseline. For phase II: The sample size was calculated based on our preliminary study described above for training-related improvement in balance (quantified by CoM sway area in medial-lateral direction during eyes-open stance), fear of falling (quantified by FES-I), and cognitive function (quantified by TMT) post exercise in people with confirmed amnestic MCI. Our preliminary results suggested that prior Exergame, COM sway in was 1.60 ± 0.76 cm² and was improved to 1.05 ± 0.44 cm² post Exergame intervention (Cohen's effect size $d=0.83$). Assuming a pairwise comparison using t-test, 80% power, alpha of 5%, 14 subjects should be sufficient to observed significant difference in balance compared to baseline. Our preliminary study has also suggested that FES-I was significantly improved post exercise compared to baseline with an effect size of 1.14, suggesting a sample size of 9 to

observe benefit for fear of falling. Finally, effect size for improvement in TMT A post exercise was 0.42. Thus using similar assumptions described above, the needed sample size for observing benefit for cognitive function is 46. Assuming approximately 10% drop out, we plan to recruit 50 subjects per group, for a total of 100 subjects.

G2. Data Analysis

Provide a description of your plan for data analysis. State the types of comparisons you plan (e.g. comparison of means, comparison of proportions, regressions, analysis of variance). Which is the PRIMARY comparison/analysis? How will the analyses proposed relate to the primary purposes of your study?

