(For both phases) We will used paired t-test (for normally distributed outcomes) and Mann-Whitney U-tests (for non-parametric outcomes) to determine the effect of intervention at 6 weeks. To examine whether the benefit of exercise is dependent on sex (sex as biological factor), we will compare the gain in balance improvement between male and female using Mann-Whitney U-test. We recognize that the study is under power for assessing the effect of confounders (e.g. age, baseline cognitive performance, baseline motor performance, BMI, etc). However, we determine whether the magnitude of gain is correlated with any of these confounders using Spearman correlation of coefficient change. During Phase II, these confounders will be controlled as covariant and between and within group comparisons will be adjusted.

Section H: Potential Risks/Discomforts

H1. Potential Risks/Discomforts

Describe and assess any potential risks/discomforts; (physical, psychological, social, legal, or other) and assess the likelihood and seriousness of such risks:

The measuring systems including LEGSys (for assessing gait and balance), BalanSens (for assessing balance), and PAMSys (for monitoring spontaneous daily physical activities) , as well as the iTMT platform are battery-powered, self-contained units and used in many clinical studies including patients with MCI and AD, and no adverse report were reported. Except activity monitoring, the rest of assessments including gait and balance will be performed in a control environment. As these devices are attached using elastic straps, research staff will ensure these are comfortably tight on the participant to avoid any pain or poor blood flow.

For home assessment, PAMSys (will be used for daily physical activity monitoring and daily motor performance such as postural transition) is worn in a shirt or vest pocket and does not rest directly against subjects' skin. Thus, wearing the PAMSys, poses no risks to subjects. All wearable sensors, which will be used in this study meet the requirements for IDE exemption under 21 CFR 812.2(c), Category 3.

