This is a longitudinal study of 'care-as-usual' with supplementary minimum risk virtually guided foot and ankle motor-cognitive exercises. We believe that there are no significant psychological, legal, or social risks. Participation is entirely voluntary and the participants could stop/leave the study at any time. All exercise programs are administered while standing but the subject will have a research staff member or caregiver (during Phase II, remote intervention arm) and thus potential risk of fall is minimum. However, like any exercise, some may feel joint pain associated with consecutive foot and ankle joint rotation. To minimize the fatigue and risk of joint pain, exercises are divided to several blocks of maximum 5 min. Subjects will have enough rest before initiating the next block of exercise. There may be some concerns or stress due to potential "failure" to successfully complete an exercise task. To minimize the risk, the first few sessions include simple motor-cognitive tasks and the complexity level increases as the exercise progresses. In our pilot program, in which 7 subjects participated in the Exergame intervention program (twice per week for 4 weeks), only one subject was dropped out due to travelling difficulties, while all other participants completed all exercise sessions. No adverse events or concerns about difficulties of the exergame tasks were reported.

Please note that there is also the possibility for loss of confidentiality. The PI and the research team will minimize the possibility of for loss of confidentiality by keeping all the physical data locked in cabinets only accessible to the research team. The electronic data will be kept on network password protected institutional computers. . Data collected during the study may be published and made publicly available. Data may also be shared with other research groups. However, data that could in any way identify the subject will not be made public or shared. And, subject PHI will be coded as much as possible to minimize the potential for loss of confidentiality.

H2. Data and safety monitoring plan

Do the study activities impart greater than minimal risk to subjects?

No

H3. Coordination of information among sites for multi-site research

Is the BCM Principal Investigator acting as the SPONSOR-INVESTIGATOR for this multi-site research?

No or Not Applicable

Is BCM the COORDINATING CENTER for this multi-site research?

No or Not Applicable

Section I: Potential Benefits

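### The tests named for Phase II cannot deliver the covariate-adjusted arm comparison that G2 promises, and no rule covers missing assessments

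*Combined protocol and SAP*

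**What the plan says.** In a sentence that covers both phases, G2 (Data Analysis) opens with: "We will used paired t-test (for normally distributed outcomes) and Mann-Whitney U-tests (for non-parametric outcomes) to determine the effect of intervention at 6 weeks". After noting limited power to study confounders, which it lists as "age, baseline cognitive performance, baseline motor performance, BMI, etc", it adds: "During Phase II, these confounders will be controlled as covariant and between and within group comparisons will be adjusted". No ANCOVA, regression or mixed model is named anywhere. No section gives an analysis population, an intention-to-treat rule or a method for missing data.

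F1 and F2 describe Phase II as a randomised comparison of 100 people over 12 weeks and 24 sessions. The control arm exercises in person and the intervention arm remotely. Assessments follow at 6 and 12 weeks and at 6 and 12 months.

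On attrition, G1 allows about 10% dropout overall, not split by arm. The background before Section D says that people whose movement and cognition are poor "generally cannot have regular visits to a rehabilitation center for face-to-face exercise, have highest drop out because of functional limitations". H1 reports that in the seven-person pilot "only one subject was dropped out due to travelling difficulties".

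**The concern.** Phase II is randomised, so its central result should be a difference between arms, and G2 says this will be adjusted. An analyst who follows the named tests gets something else: a pre-post change within each arm from the paired t-test, or an unadjusted rank comparison from Mann-Whitney. To honour the adjustment sentence, the analyst must choose a model, its covariates and its handling of missing values after the fact.

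Two things are at stake. The first is an arm estimate that depends on unrecorded choices. The second is the benefit of the baseline data already being collected: precision, and protection if people with worse baseline function are lost more often from one arm.

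**Working it through.** **1. What the promise needs and what the named tests give**

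| Needed in Phase II | Paired t-test | Mann-Whitney U |
|---|---|---|
| Compares randomised arms | No, compares each person with their own baseline | Yes, if applied to arms |
| Takes covariates | No | No |
| Uses people without the analysed follow-up value | No | No |

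Neither column delivers an adjusted between-arm comparison. This step needs no assumptions.

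**2. The plan's own figure**

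G1 says "effect size for improvement in TMT A post exercise was 0.42" and that "the needed sample size for observing benefit for cognitive function is 46". A two-sided 5% paired t-test with 80% power at d = 0.42 needs 46.5 people, so 47; power at 46 is 79.6%. The figure reproduces within rounding, as a within-group pre-post calculation. G1 gives no between-arm effect.

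**3. How large could selective loss be?**

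All inputs except the 10% overall dropout are assumptions:
- no true arm difference;
- standardised baseline function X, with a logistic chance of dropout that rises as X falls, slope s = 0.7 to 1.0 per SD;
- correlation ρ of 0.3 to 0.5 between baseline and change;
- dropout of 12% control and 8% remote, or 15% and 5%. Both pairs average 10%.

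Bias of the unadjusted comparison = ρ × (mean X of retained controls − mean X of retained remote participants), in SDs of change.

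| Dropout, control / remote | Gap in mean X (s = 0.7; 1.0) | Bias, ρ = 0.3 to 0.5 |
|---|---|---|
| 12% / 8% | 0.026; 0.034 | 0.008 to 0.017 |
| 15% / 5% | 0.065; 0.086 | 0.019 to 0.043 |

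So the bias is about 0.01 to 0.04 SD. With 45 per arm (50 × 0.9) the standard error is √(2/45) = 0.211 SD. A bias of 0.04 is 0.19 standard errors and raises a two-sided 5% error rate to about 5.4%. At much heavier assumed loss (20–30% control, 5–10% remote) the same formula gives about 0.02 to 0.10 SD. The sign reverses if people with worse baseline function gain more, or if the remote arm loses more.

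A linear model containing X has zero bias here. That is built in, because dropout was made to depend on X alone; it does not test the missing-at-random assumption.

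**4. What baseline adjustment gains in precision**

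Let r be the correlation between baseline and follow-up of the same outcome, with equal variances. Variance of change = 2σ²(1 − r). Variance after adjustment = σ²(1 − r²). The ratio is (1 + r)/2. With 45 per arm, the difference detectable with 80% power is 0.60 SD of change unadjusted; multiply by √((1 + r)/2) for the adjusted figure.

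| Assumed r | Variance ratio | Detectable difference (SD of change) | Power if the arm difference were 0.42 SD |
|---|---|---|---|
| unadjusted | 1 | 0.60 | 50% |
| 0.3 | 0.65 | 0.48 | 69% |
| 0.5 | 0.75 | 0.52 | 62% |
| 0.7 | 0.85 | 0.55 | 57% |

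The power column only illustrates the gain in precision. The documents' 0.42 is a within-group change, both arms receive the same exercise programme, and no section anticipates an arm difference of that size.

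**The case against.** The strongest reply is that G2 already promises adjustment, and its list includes baseline cognitive and motor performance. An analyst who keeps that promise would fit something like ANCOVA, which removes the bias in step 3 and secures much of the gain in step 4. F1 also classes the study as a pilot. This largely stands. Those figures describe what happens if the named tests are followed literally, not the analysis the adjustment sentence intends. What remains is that no model is named to carry out the intention, that the baseline of the outcome itself is not clearly included (baseline FES-I, for instance, is not listed), and that missing assessments are not addressed.

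A reader might go further and infer that the protocol expects the in-person arm to lose its worst performers, so that the arm comparison is biased. The documents do not support that:
- The background statement is general and not a forecast by arm. The same sentence says these people also adhere worst to unsupervised exercise, although the remote arm is to be supervised remotely.
- The pilot evidence is one person, with nothing linking the travel problem to poor function.
- Eligibility excludes MoCA below 20 and major mobility disorders. Section I pays control-arm parking or transport (up to $50) and $10 per exercise session.
- Missing a session is not missing an assessment. Section I has the remote arm attending baseline and post-exercise evaluations too, and no section says that people who stop sessions will not be assessed.

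Nor does the plan state a completers-only analysis. The exclusion of people without a follow-up value follows from the paired test and the silence on missing data.

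**Conclusion.** The point holds as a gap between the promised analysis and the named methods: the Phase II adjusted arm comparison cannot be obtained from a paired t-test or a Mann-Whitney test. That conclusion rests on the text alone.

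The attrition part is secondary. Function-related loss, possibly unequal by arm, is plausible, but its size and direction cannot be derived from the documents. At the planned 10% overall dropout, the bias in an unadjusted comparison would probably be small, about 0.01 to 0.04 SD under the stated assumptions. The gain in precision is more dependable: variance falls to between 0.65 and 0.85 of the change-score variance for assumed r of 0.3 to 0.7. The change should be made before Phase II data are analysed, but the point does not show that the arm comparison would be materially biased or that the stated sample-size arithmetic is wrong.

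**What to change.** For Phase II, replace the named tests in G2 with one baseline-adjusted linear model per outcome:
- **Model:** a linear mixed model over the scheduled visits, or ANCOVA at the analysed visit.
- **Population:** all randomised participants with outcome data, in their assigned arm.
- **Terms:** arm (plus visit and arm-by-visit in the mixed model), the baseline value of that outcome, and the covariates G2 already lists. State the list in full, without an open-ended ending.
- **Skewed outcomes:** transform where needed, for example the log of Trail Making time.
- **Report:** the arm difference with its confidence interval.
- **Missing data:** state the missing-at-random assumption, and invite people who stop sessions to the assessment visits already scheduled.

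Which visit should carry the main result is a separate question; either model works at the visit chosen. The cost is a paragraph of wording and modest programming, with no extra participants or visits. The downside is the missing-at-random assumption, which the data cannot verify.

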Category 1: Research not involving greater than minimum risk.

E2. Subjects

Gender:
Both

Age:

Geriatric (65+ yrs)

Ethnicity:

All Ethnicities

Primary Language:

English, Spanish

Groups to be recruited will include:

Patients

Which if any of the following vulnerable populations will be recruited as subjects?

Vulnerable populations require special protections. How will you obtain informed consent, protect subject confidentiality, and prevent undue coercion?

E3. Pregnant woman/fetus

Will pregnant women and/or fetuses (as described in 45 CFR 46 Subpart B) be enrolled in the research?

No

E4. Neonates

Will neonates of uncertain viability or nonviable neonates (as described in 45 CFR 46 Subpart B) be enrolled in the research?

No

E5. Children

Will children be enrolled in the research?

No

Section F: Design/Procedure

F1. Design

Select one category that most adequately describes your research:

c) Pilot

Discuss the research design including but not limited to such issues as: probability of group assignment, potential for subject to be randomized to placebo group, use of control subjects, etc.

For this research design there are two phases.

Phase I: 15 subjects with mild dementia and cognitive impairments will participate in a single arm 6 weeks remote exercise intervention.

Phase II: 100 subjects with mild dementia and cognitive impairments will participate in a randomized controlled trial (RCT) exercise intervention using two arms for 12 weeks. The control group will perform the exercise intervention in a supervised condition and the intervention group will perform the exercise intervention remotely.

Inclusion Criteria:

Male and female patients with MCI and mild dementia (formal diagnosis or MoCA score between 20-26), who are ambulatory (able to walk a distance of 20m with or without walking assistance), living independently in a residential home with a caregiver/informant, and who are willing and able to provide informed consent, will be recruited.

Exclusion Criteria:

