Subjects will be excluded if they have a immobility or major mobility disorder or inability to engage safely in the proposed weight-bearing exercise program (e.g., double amputees, patients with active plantar ulcers, patients with major back or lower extremity pain). If they are diagnosed with severe cognitive impairment (MoCA score < 20), other neurological conditions associated with cognitive impairment such as stroke, Parkinson disease, and head injury, and/or any clinically significant psychiatric condition, current drug or alcohol abuse, or laboratory abnormality that would interfere with the ability to participate in the study. Subjects with major hearing/visual impairment will also be excluded.

F2. Procedure

Prior to any study related procedures, all subjects will be consented.

These are the study procedures,

Phase I: The study will consist of a 6 week exercise program with one baseline, 12 at home intervention sessions, 3 weeks follow up, and 6 weeks follow up.

History and Physical Examination: A standard physical examination will be performed at screening. We will record age, gender, presence of diabetes and its type and duration, diabetic treatment, prior foot ulcers (with location and duration), prior amputations or foot surgeries, co-existing medical conditions, and location and duration of the ulcer. We will use Kaplan Co-morbidity Index to score disease severity.

Medical History: We will record socio-demographics (e.g. age, gender, BMI, education, marital status, etc) and medical history (health status including comorbidities, history of falls, history of hospitalization, prior surgery, duration of diagnosed as MCI, co-existing medical conditions, hearing and visual performance, frailty status, etc), medication use, etc. We will examine frailty status using Fried Frailty criteria (Weight loss >10 pounds in preceding year; Grip strength; Low levels of physical activity; 15 foot walk time; Exhaustion). Standard foot questionnaire will be used to assess any potential limitation, which may influence the ability of participants to perform iTMT using ankle-foot trail making. Foot sensation and peripheral neuropathy will be examined using Vibration Perception Threshold (VPT) testing. We will administer the valid and reliable eMINI to exclude individuals with substance use, bipolar, and psychotic disorders. We will document all prescriptions and over-the-counter medications. We will measure height and weight to determine body mass index.

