Phone calls: We will contact subjects at three and six months after their follow up visit to ask if they have had any accidental falls and other questions regarding their health. Research Coordinators may also call subject for study related questions.

Photos and media: We will be asking permission of the subject to take photos, film videos and/or record audio during the visits in order to monitor their progress throughout the study. Additionally, these photographs might be used for scientific publications/ oral presentations. If the subject's face is in the photo, as per journal policy, we will cover their face.

Phase II: The study will consist of a 12 week exercise program with one baseline, 24 exercise sessions, 6 weeks follow up, 12 weeks follow up, 6 months follow up, and 12 month follow up.

The same questionnaires and physical assessments will be completed at each in person visit as Phase I. In Phase II, 100 subjects will be randomized into either intervention or control group. All recruited subjects will undergo to 12 weeks exercise program using the Exergaming platform described in the proposal, twice per week for approximately 30 minutes. The intervention group will be given the Exergaming system and will perform the 24 exercise sessions remotely. The control group will perform the exercise sessions in person under supervision with the Exergaming system. The first four sessions (week #2), subjects are asked to perform six blocks (each approximately takes 5 min to be completed) of consecutive ankle reaching tasks in upward-downward (i.e. ankle flexion-extension) direction and side-ward reaching task (foot inversion-eversion). They could have reset between each block of exercise before starting the next block. Starting the 5th session (week #4), reaching tasks on diagonal directions are added, which is required the combined foot inversion-eversion and ankle flexion-extension. To keep the duration of exercise constant, a block from simple reaching task is replaced by a new complex reaching task. From the 11th session (week #6), motor-cognitive tasks as described in the following will be added. The tasks make the program more challenging and fun, in addition to potentially having a secondary benefit for older patients who may struggle to execute motor-cognitive tasks.

Section G: Sample Size/Data Analysis

G1. Sample Size

How many subjects (or specimens, or charts) will be used in this study?

Local: 115 Worldwide: 115

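### The analysis section dates the intervention test at 6 weeks for both phases, but in Phase II that is session 12 of 24, and no analysis is tied to the 12-week visit

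*Combined protocol and SAP*

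**What the plan says.** The first sentence of the answer under G2 (Data Analysis) covers both phases. It begins "For both phases) We will used paired t-test"; this is the test planned where the outcome has a normal distribution. The rank-based alternative is the Mann-Whitney U-test, and the sentence ends with the date: "for non-parametric outcomes) to determine the effect of intervention at 6 weeks". No other time point appears in G2. One sentence there is specific to Phase II: "During Phase II, these confounders will be controlled as covariant and between and within group comparisons will be adjusted". It names no visit. The form's question for G2 asks which analysis is primary, and the answer does not name one.

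The two phases differ in length. F2 describes Phase I as follows: "The study will consist of a 6 week exercise program with one baseline, 12 at home intervention sessions", with visits at 3 and 6 weeks. For Phase II, F1 says that 100 subjects "will participate in a randomized controlled trial (RCT) exercise intervention using two arms for 12 weeks", and F2 gives the schedule: "The study will consist of a 12 week exercise program with one baseline, 24 exercise sessions, 6 weeks follow up, 12 weeks follow up", followed by visits at 6 and 12 months. Sessions are twice weekly in both phases. F2 also stages the Phase II content: "From the 11th session (week #6), motor-cognitive tasks as described in the following will be added". Section I mentions an evaluation after the exercise period but attaches no analysis to it.

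**The concern.** One date is applied to two programmes of different length. It fits Phase I. In Phase II it falls halfway through the exercise that participants are randomised to receive, either remotely or under supervision. A reader who carries out G2 literally would test the Phase II intervention before half of it has been given and would have no instruction for the visit at which it ends.

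Two things are at stake. The first is which effect the dated test estimates: six weeks of a 12-week programme, or the programme itself. The second is whether the visit for the adjusted between-group comparison is fixed in advance, since Phase II schedules four visits after baseline.

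**Working it through.** **Inputs.** Session frequency, programme lengths, session totals and visit schedules come from F1 and F2, and the analysis date from G2. Visit weeks are counted from baseline. This fits Phase I, where the 6-week visit closes a 6-week programme, and the consent-form titles in Section Q, which call Phase I a 6-week and Phase II a 12-month programme. Sessions are assumed to run on schedule.

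**1. Reproduce the plan's session totals** (sessions = sessions per week × weeks).
- Phase I: 2 × 6 = 12, as stated.
- Phase II: 2 × 12 = 24, as stated.

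**2. Sessions delivered by week 6.**
- Phase I: 12 of 12 = 100%.
- Phase II: 2 × 6 = 12 of 24 = 50%.

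**3. Motor-cognitive sessions in Phase II by week 6.** On the F2 schedule these start at session 11. Sessions 11 to 24 number 24 − 11 + 1 = 14. By week 6 only sessions 11 and 12 can have taken place, so at most 2 of 14 = 14%. This count is less firm than the one in step 2, for two reasons.
- The week labels in F2 are not consistent. At two per week, session 11 falls in week 6 (11/2 = 5.5, rounded up), which agrees with its label. Session 5 falls in week 3 (5/2 = 2.5, rounded up) but is labelled week 4.
- H1 describes the opening sessions as already containing easy motor-cognitive tasks, which sits uneasily with a start at session 11.

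**4. The adjusted Phase II comparisons.** Two readings are possible.
- *The 6-week date in the lead sentence governs the whole paragraph.* The adjusted comparisons are then also at 12 of 24 sessions, and there is no choice of visit.
- *The sentence is undated.* The visit could then be chosen among four: "6 weeks follow up, 12 weeks follow up, 6 months follow up, and 12 month follow up".

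Only the second reading needs an error-rate illustration. Take k visits, each tested at two-sided 5%, with no true effect and an equal correlation r between the test statistics. The chance of at least one significant result is

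1 − ∫ φ(u) · [Φ((1.96 − √r·u)/√(1−r)) − Φ((−1.96 − √r·u)/√(1−r))]^k du.

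| Visits to choose from | r = 0.9 | r = 0.8 | r = 0.5 |
|---|---|---|---|
| 2 (weeks 6 and 12) | 7.0% | 7.8% | 9.1% |
| 4 (all follow-ups) | 9.4% | 11.4% | 15.6% |

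The documents give no correlation between visits, so r is an assumption. The figures are for one outcome.

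**The case against.** **The 6-week date may simply be carried over from Phase I, and the Phase II sentence may be meant to cover week 12.** Both are possible, and a 12-week analysis is unspecified rather than excluded. But G2 puts both phases under the 6-week date and says nothing about week 12, so the intention cannot be read from the plan.

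**Two inferences from G1.** A reader might infer that G1 sizes Phase II on a week-12 change, so that the sized effect and the dated test disagree. The documents do not support this. The post-exercise improvements in G1 are those of the preliminary study, whose programme lasted 4 weeks at two sessions a week (G1 and H1), or 8 sessions. That is nearer to the 12 sessions of week 6 than to the 24 of week 12, and G1 never sizes a week-12 change. For the same reason a reader should not infer that week 6 is too early to see an effect. Nothing in the documents shows that.

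**The false-positive rates are hypothetical.** This stands in part. They measure an unnamed visit, not the 6-week date itself. They apply only if the adjusted comparison is undated and the visit is chosen after the results are seen.

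**Both arms follow the same schedule, and the form classes the study as a pilot.** The shared schedule means that no between-arm bias follows, and none is claimed. The pilot label lowers the stakes. Phase II is nevertheless a 100-subject randomised comparison, with a sample size calculated at 80% power and 5% alpha, so its time point should be fixed.

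**Conclusion.** The concern holds in a limited form and should be fixed. The single date in G2 fits Phase I and misses the end of the Phase II programme by six weeks and 12 sessions. The only dated Phase II test therefore does not estimate the effect of the 12-week programme, and the visit that could do so has no analysis attached.

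The firm measure of size is 12 of 24 sessions, which needs only the stated frequency and total and visit weeks counted from baseline. The 2-of-14 count for motor-cognitive sessions depends on an F2 schedule that is not fully consistent with itself or with H1. Both are counts of exercise delivered, not estimates of lost effect. The ranges of 7.0% to 9.1% and 9.4% to 15.6% are illustrations conditional on the undated reading, on selection of the visit after the results, and on the assumed correlations.

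**What to change.** In G2, state the time point by phase.

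- **Phase I:** 6 weeks, as now.
- **Phase II:** within-group and adjusted between-group comparisons at the 12-week end-of-programme visit as the main time point; the 6-week analysis kept as additional and non-primary; the role of the 6- and 12-month visits stated.
- **If week 6 is meant to be the main Phase II time point:** say so, with the reason, before the data are analysed.

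The change takes a few lines of text and no new data, because the 12-week visit is already scheduled. The downside is any extra dropout between weeks 6 and 12. As an illustration, take 45 completers per arm (the 10% dropout in G1 applied to 50) against 40 (20%, an assumption). An unadjusted two-sample t-test with 80% power at two-sided 5% then detects 0.60 SD against 0.63 SD. G1 does not say at which visit its 10% applies and gives no between-group effect size to compare with these values.
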